6 STUDY PROCEDURES

6.1 Study Procedures

The Study Diagram in Section 5 summarizes the study procedures to be performed at each visit. Individual study procedures are described in detail below. It may be necessary to perform these procedures at unscheduled time points if deemed clinically necessary by the investigator. Furthermore, additional evaluations/testing may be deemed necessary by the Sponsor for reasons related to subject safety.

6.1.1 Administrative Procedures

6.1.1.1 Randomization and Study Invitation

In the study, 5 geographic regions will be identified as 'clusters' at the first stage. Within a region, a computer-generated randomization list by stratum (age) will then be produced separately in each participating site to identify and select specific invitees. All possible resources securing the participant's bio-information and contact details will be utilized to generate a full list of potential invitees. These resources include, but not limited to, Government resident lists, community-dwelling records, city council records, primary care health records and/or local health insurance records. Based on the sequence of the list, a numbered letter will be sent out to all women who are 50 years of age (inclusive) or above from the investigator to enquiry of their wish to attend the study. The letter to the women selected will explain the nature, the objectives and the study elements of the study. The receipt and acceptance of invitation will direct to the investigators by telephone, email, return of letter, or showcase the letter at the time of onsite screening. An advance notification by telephone or email may be practiced by the site investigator and/or study authorized staff to increase the rate of invitation acceptance.

6.1.1.2 General Informed Consent

Consent must be documented by the subject's dated signature or by the subject's legally acceptable representative's dated signature on a consent form along with the dated signature of the person conducting the consent discussion.

A copy of the signed and dated consent form should be given to the subject before participation in the study.

The initial informed consent form, any subsequent revised written informed consent form and any written information provided to the subject must receive the IRB/ERC's approval/favorable opinion in advance of use. The subject or his/her legally acceptable representative should be informed in a timely manner if new information becomes available that may be relevant to the subject's willingness to continue participation in the study. The communication of this information will be provided and documented via a revised consent form or addendum to the original consent form that captures the subject's dated signature or by the subject's legally acceptable representative's dated signature.

Specifics about a study and the study population will be added to the consent form template at the protocol level.

The informed consent will adhere to IRB/ERC requirements, applicable laws and regulations and Sponsor requirements.

6.1.1.3 Medical History

A medical history will be obtained by the investigator or qualified designee. A brief review of the subject's medical history, including menstrual history, physical ability and cognitive status, based on the subject's medical records and physical examination, will be performed to determine study eligibility at the screening.

6.1.1.4 Assignment of Screening Number

All consented subjects will be given a unique screening number that will be used to identify the subject before all study-related procedures. Each subject will be assigned only one screening number. Screening numbers must not be re-used for different subjects. Any subject who is screened multiple times will retain the original screening number assigned at the initial screening visit. No separate study ID number will be allocated to the eligible participants.

6.1.2 Clinical Procedures/Assessments

6.1.2.1 Questionnaire and Physical Examination

The study's questionnaire will be developed based on questionnaires of previous large studies [29-34] and is attached in the Section 11 Appendices. During the investigator's meeting and training session, the questionnaire will be reviewed and discussed in order to clarify terms, country features, and standardization. The investigator will have training in understanding the questionnaire before the study enrollment. The questionnaire will be delivered by Chinese simplified written language. In order to minimize variability, it is preferred that the same individual investigator (s) perform questionnaire interviews for all subjects at each study site.

The questionnaire will collect self-reported data on demographics, gynecological history, socioeconomic status, life style factors, and clinical risk factors for osteoporosis. Commercial calcium supplement and vitamin D intake will be calculated according to names and daily doses reported by participants. Alcohol intake will be calculated in grams per day and be categorized according to the WHO as: never, for the subject who does not report alcohol intake; mild, from 1 to 10 grams per day; moderate, from 11 to 40 grams per day; and severe, for more than 40 grams per day. For smoking history, information on time and average number of cigarettes (and any other type of tobacco) consumed will be obtained. Physical activity will be assessed in minutes per day according to time spent on various activities including walking, dancing, and other Chinese specific outdoor activities.

All other major risk factors will be based on self-reported during the interview administered by the investigator. The subject's symptoms/signs and medical records will be reviewed for possible medical history. Comorbidities including asthma, chronic obstructive pulmonary disease (COPD), and diabetes mellitus are defined in the study (Refer to 'List of Definitions') and all definitions of diseases will be provided and further explained by the investigator during the interview. A detailed history of any fracture (after age of 40, anatomical site and the level of trauma) and height loss will be collected; prior and concomitant medications regarding steroids use, hormone replacement therapy (HRT), and any use of antiresorptive drugs will be recorded for medication name, daily dose and treatment duration.

Standing height (centimeters) will be determined by means of a stadiometer and weight (kilograms) assessed with a regularly calibrated scale at each site. The stadiometer should be adequate to measure height within 4 mm. Patients will be weighed without shoes or jackets. The BMI will be computed as weight (kilograms) divided by the square of the height (square meters) and defined as underweight \leq 18.5, normal (18.5–24.9 kg/m²), overweight (25 to 29.9 kg/m²), and obese ($>$ 30 kg/m²). The subject will be asked to recall and report the height and weight at the age of 25. In addition, a fracture-related physical examination will be performed for the subject who has reported a fracture history, based on the investigator's discretion.

The questionnaire should also be reviewed by the investigators for any SAEs/drug-related AEs that need to be reported per the protocol.

6.1.2.2 DXA Examination

All subjects are expected to have BMD measurement upon a successful completion of questionnaire. Densitometric measurement will be performed by a central dual-energy x-ray absorptiometry device at each site. DXA scanners from different manufacturers including Hologic, Lunar and Norland will be used onsite upon availability. A peripheral DXA on mobile health van must not be used in the study. BMD from all subjects included in a particular site will be measured by the same DXA machine or, at least, a machine from the same manufacturer. All BMD results from different machines will be quality controlled during the study.

On the day of the exam, the subject will be instructed to position and wear properly under a low X-ray radiation exposure. The subject will lie on a padded table, where legs will be supported on a padded box to flatten the pelvis and lumbar spine, and foot be placed in a brace that rotates the hip inward. Detailed positioning and other instructions will be suggested by the study DXA technicians according to the manufacturer's operation manual.

At the investigator's discretion, the subject's DXA measurement may be made on an unscheduled follow-up if there is any compelling reason (i.e. injected contrast materials or device failure) precluding the examination on the day of the study visit. The subject's BMD results from any institution 28 days prior to screening may be deemed appropriate for the study if such measurements are made per protocol as assessed by the investigator and discussed with the Sponsor. Subjects with known spine deformities will be required

to have densitometric measurement unless a waiver is made by the investigator after a consultation with the Sponsor.

6.1.2.3 Radiology and Fracture Diagnostic Procedure

The subject will be required to have an examination on the spine. The radiographs will be obtained using a standardized technique in the all participating sites. Two lateral radiographies centered on T7 and L2 will be performed. Radiographs may be taken with the patient in the left lateral position. For the lateral thoracic spine the cassette is positioned with the top above the subject's shoulders. To maintain lateral position, the subject's shoulders, hips, knees and ankles will be superimposed with padding between the elbows and knees. A radiolucent pad may be required under the lumbar spine at waist level to straighten the lower thoracic spine. For thoracic film taking, the subject will be required to breathing by instructions to allow blurring of the overlying ribs and lung detail by motion. The quality of the radiograph is improved further by placing a sheet of lead rubber on the X-ray table posterior to the spine. For the lateral lumbar spine view, T12 to S1 should be visualized on the radiograph in the true lateral position without rotation or obliquity. As with the lateral thoracic view, the subject's shoulders, hips, knees and ankles will be superimposed, padding between the elbow, knees and ankles. The lumbar spine must also be parallel to the film. Radiolucent pads may be placed under the upper part of the lumbar spine to correct an oblique direction from L1 to L5. Alternatively, the X-ray tube can be angled toward the feet so that the X-ray beam is perpendicular to the spine.

The Genant semiquantitative method will be used to standardize the diagnosis of fractures, as recommended by the IOF. Prior to the study, each site will forward sample radiographs to the radiology coordination site, as nominated by the Sponsor, for quality assessment and to check compliance with the protocol and technical standard. Two experienced radiologists, blinded to the study, will perform the adjudicative evaluation of the radiographs. Intra- and inter-observer reliabilities will be tested using first 100 X-ray images from any study site before the results interpretation. In case there is a disagreement in terms of Genant's grading between experienced radiologists, a third party radiological review will be performed to give a final decision.

6.1.3 Other Procedures

6.1.3.1 Withdrawal/Discontinuation

When a subject discontinues/withdraws prior to trial completion, all applicable activities scheduled for the final trial visit should be performed at the time of discontinuation. In the study, the subject will have one scheduled visit and have the right to discontinue at any time of the study, which is included in the letter of invitation and informed consent. No specific activities for the subject will be arranged at the time of the subject's withdrawal.

Product: MK-0217A
Protocol/Amendment No.: 911

6.1.4 Visit Requirements

Visit requirements are outlined in Section 5 – Study Diagram. Specific procedure-related details are provided above in Section 6.1 – Study Procedures.

6.1.4.1 Screening

Participants will be evaluated to determine that they fulfill the entry requirements as set forth in Sections 3.3-3.4. Screening procedures may be repeated after consultation with the Sponsor.

7 Safety Reporting and Related Procedures

7.1 Definition of Adverse Event

An adverse event is defined as any untoward medical occurrence in a patient or clinical investigation subject administered a pharmaceutical product or who undergoes a protocol-specified procedure and which does not necessarily have to have a causal relationship with this treatment or procedure. An adverse event can therefore be any unfavorable and unintended sign (including an abnormal laboratory finding, for example), symptom, or disease temporally associated with the use of a medicinal product or protocol-specified procedure, whether or not considered related to the medicinal product or protocol-specified procedure. Any worsening (i.e., any clinically significant adverse change in frequency and/or intensity) of a preexisting condition that is temporally associated with the use of the Sponsor's product, is also an adverse event.

Changes resulting from normal growth and development that do not vary significantly in frequency or severity from expected levels are not to be considered adverse events. Examples of this may include, but are not limited to, teething, typical crying in infants and children and onset of menses or menopause occurring at a physiologically appropriate time.

Sponsor's product includes any pharmaceutical product, biological product, device, diagnostic agent or protocol-specified procedure, whether investigational (including placebo or active comparator product) or marketed, manufactured by, licensed by, provided by or distributed by the Sponsor for human use.

Adverse events may occur during the course of the use of the Sponsor's product in studies or within the follow-up period specified by the protocol, or prescribed in clinical practice, from overdose (whether accidental or intentional), from abuse and from withdrawal.

7.2 Definition of Serious Adverse Event

"Serious Adverse Event" (SAE) means an adverse event which is fatal or life threatening, results in persistent or significant disability/incapacity, requires inpatient hospitalization, prolongation of existing inpatient hospitalization, or is a congenital anomaly/birth defect, cancer, the result of an overdose or is another important medical event. Other important medical events that may not result in death, may not be life-threatening, or may not require hospitalization may be considered a Serious Adverse Event when, based upon appropriate medical judgment, they may jeopardize the patient or subject and may require medical or surgical intervention to prevent one of the other outcomes listed previously. Examples of such medical events include allergic bronchospasm requiring intensive treatment in an emergency room or at home and blood dyscrasias or convulsions that do not result in inpatient hospitalization.

7.2.1 Other Relevant Safety Information

The following events are considered important safety information and should be collected/reported using the same timeframes and reporting methods as SAEs:

- Exposure to product during pregnancy or lactation
- Lack of effect

7.3 Causality Assessment

A causality assessment (attribution) must be performed and recorded for each SAE/non-serious AE in relationship to a Sponsor's product. During studies with direct patient contact (visits), the assessment of causality will be determined by an investigator who is a qualified physician according to his/her best clinical judgment. Use the following criteria as guidance (not all criteria must be present to be indicative of causality to a Sponsor's product): There is evidence of exposure to the Sponsor's product; the temporal sequence of the AE onset relative to the administration of the Sponsor's product is reasonable; and the AE is more likely explained by the Sponsor's product than by another cause. In studies without direct patient contact, the assessment of causality would be determined by a notation of attribution in medical records. Causality can be assigned by the investigator or the Sponsor. Examples include a drug-induced rash that an investigator attributes to a specific product, or a clinical notation that a product was discontinued because it caused insomnia.

7.4 Adverse Event Reporting

Any Serious Adverse Event (SAE), regardless of causality, which occurs in any study subject within 2 days following a protocol-specified procedure, must be recorded in the study database and also must be submitted to Global Safety. Additionally, any SAE brought to the attention of an investigator at any time after the above specified time period must be recorded in the study database and also must be submitted to Global Safety if the event is felt to be possibly related to a protocol-specified procedure. All subjects with SAEs related to protocol-specified procedures must be followed up for outcome. All non-serious AEs which are felt to be possibly related to the protocol-specified procedure must be recorded in the study database and also must be submitted to Global Safety. In such cases, the INVESTIGATOR will complete an Adverse Event report form (attachment) in English and submit SAEs within 24 hours and non-serious AEs within 10 calendar days to the Vendor Sponsor Contact by Fax or e-mail. Vendor Sponsor Contact will submit AE form to Merck Global Safety at AER [contact] (US), or toll-free [contact] (ex-US and US availability) within 2 business days (SAEs) and 10 calendar days (AEs) of receipt for reporting to worldwide regulatory agencies as appropriate.

In addition, if through the conduct of this study, an investigator becomes aware of any Serious Adverse Event (SAE), regardless of causality, or non-serious AE, that is felt to be

Product: MK-0217A
Protocol/Amendment No.: 911

causally related, to any investigational or marketed product manufactured by Merck the event must be reported. In such cases, the INVESTIGATOR will complete an Adverse Event report form (attachment) in English and submit SAEs within 24 hours and non-serious AEs within 10 calendar days to the Vendor Sponsor Contact by Fax or e-mail. Vendor Sponsor Contact will submit AE form to Merck Global Safety at AER [contact] (US), or toll-free [contact] (ex-US and US availability) within 2 business days (SAEs) and 10 calendar days (AEs) of receipt for reporting to worldwide regulatory agencies as appropriate.

The end of study report summarizing SAEs and non-serious AEs to study procedures will be provided to regulatory agencies as required.

Spontaneously reported SAEs and non-serious AEs following the use of OTHER investigational or marketed products manufactured by Merck, regardless of causality, will be collected and reported to regulatory agencies as individual cases as required but will not be included in the end of study report.

7.5 Sponsor Responsibility for Reporting Adverse Events

All adverse events will be reported to regulatory agencies, IRB/IECs and investigators in accordance with all applicable global laws and regulations.

8 Statistical Analysis Plan

8.1 Statistical Methods

This section outlines the statistical analysis strategy and procedures for the study. If, after the study has begun, changes are made to primary and/or key secondary hypotheses, or the statistical methods related to those hypotheses, then the protocol will be amended. Changes to exploratory or other non-confirmatory analyses made after the protocol has been finalized, along with an explanation as to when and why they occurred, will be listed in the CSR for the study. Post hoc exploratory analyses will be clearly identified in the CSR. A separate SAP will be created for this study.

8.1.1 Primary Objective(s): Calculation of Epidemiological Measure(s) of Interest (e.g. descriptive statistics, hazard ratios, incidence rates, test/retest reliability)

The study's primary objective is to investigate the prevalence of radiographic vertebral fractures in community-dwelling postmenopausal women in China. Descriptive statistics will be made to statistically address this objective. No hypothesis testing will be applied in the study for this primary objective.

Point estimates (percentage) of prevalence by overall study population and by age group and/or geographic region will be calculated and displayed. A fracture case is defined and counted as the subject with the presence of at least one vertebra classified as grade 1, 2, or 3 semi-quantitatively by Genant's score as agreed by both study radiologists.

Point estimates of prevalence rates by overall and geographic region will be adjusted by a nationwide age distribution using the database from Basic Statistics on National Population Census 2010, National Bureau of Statistics of China [53]. A direct method of adjusting rates will be made to give age-standardized prevalence. Age-standardized rate by regional age distribution data may be calculated subject to site location and will be specified in the SAP before database lock and study analyses.

A corresponding two-sided 95% confidence interval (CI) for each individual point estimate will be given. This 95% CI is based on a direct calculation of the exact binomial distribution. A more conservative method, the Wilson Score CI [52], will be applied to give 95% CIs for all point estimates and compared with the exact binomial distribution.

To test reproducibility for fracture adjudication, intra- and inter-observer reliabilities will be tested using a sample of first 100 X-ray films from any participating site in the study. Intra-observer and inter-observer agreement will be calculated by kappa statistic. A κ is 0.81 or above suggests very good agreement.

The statistical analyses for primary objective are summarized in Table 8.1.1.1.

Table 8.1.1.1 Statistical Analysis Approaches on Primary Objective

VF Prevalence	Rate	Estimate*
Overall	Crude/Age-Standardized Rate	Point and 95% CI
Age Group§	Crude Rate	Point and 95% CI
Region^	Crude/Age-Standardized Rate	Point and 95% CI
Age Group and Region△	Crude Rate	Point and 95% CI
Genant's Grade※	Crude Rate	Point and 95% CI

* Based on exact binomial distribution 95% CI and Wilson Score 95% CI;
§ Age group will be given by 50 – 54, 55 – 59, 60 – 65, 65 – 69, 70 – 74, 75 – 79, and 80+; and by < 65 and ≥ 65;
^ Participating sites will be grouped by 5 regions in China: North, South, Southeast, Southwest, and Central;
△ Prevalence rate will be presented by all age groups and overall in individual regions in China;
※ Genant's Grade by 1, 2 or 3.

8.1.2 Secondary Objective(s): Calculation of Epidemiological Measure(s) of Interest (e.g. hazard ratios, incidence rates, test/retest reliability)

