3 METHODOLOGY

3.1 Summary of Study Design

This study will be designed as an observational, population-based, cross-sectional study. A total of 2700 postmenopausal women over age of 50 inclusive and physically living in a community will be included in the study. As suggested by Chinese local guideline, postmenopausal women are eligible for a subsidized screening program (blood chemistry, radiology and/or DXA assessment) for osteoporosis clinical management. A cluster sampling (two-stage random sampling) by age and geographic region will be performed to represent a geographically generalized Chinese population with specific gender and age groups relevant to postmenopausal osteoporosis and VF prevalence. Subject recruitment will be based on various local demographic records including Government resident lists, local population lists, electoral registers, and health registers by a study invitation and a referral to the investigators at each study center. By 1 onsite visit, an interview, DXA measurement, and thoracic/lumbar spine X-ray will be performed to collect a set of data regarding socioeconomic/medical (interview-based questionnaire), VF assessment (radiographs), and specific densitometric information (BMD DXA) from the participant. No follow-up visit is required for this cross-sectional study unless a spine imaging and/or BMD measurement cannot be made during the visit due to a particular reason in the study or from the subject. The recruitment period is estimated between 6 and 9 months and initiated at any time point during a calendar year, because a seasonal or social impact on the data of interest is minimal. Analyses will be based on epidemiological data and then be expanded to establish a vertebral fracture risk assessment model.

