3.5 Stratification

The subjects will be sampled and stratified according to the following factors:

- 1) Age;

Seven (7) age groups: 50 - 54, 55 - 59, 60 - 64, 65 - 69, 70 - 74, 75 - 79, 80 or above;

- 2) Geographic region;

Five (5) regions in China: North, South, Southeast, Southwest, and Central

4 Variables and Epidemiological Measurements

All eligible participants will be included in the study to an endocrinologist, or other specialist, whenever appropriate, for the collection of all clinical and radiological information by 1 onsite study visit in a cross-sectional fashion. Spine radiograph and/or DXA may be separated from onsite interview by a follow-up visit as determined by the investigator.

Questionnaire

All demographic data, socioeconomic status, lifestyle information, and clinical features including medical history/concomitant medications, will be collected by an interviewer-administered questionnaire performed by the investigator. The questionnaire will be designed to adapt China's cultural and clinical practice. The analyzable variables derived from the questionnaire include (but not limited to):

- Age (absolute value and category);
- Place of birth and dwelling geographic region;
- BMI (height and weight, as measured in the site);
- Social status and lifestyle (educational level, occupation, monthly income, physical exercise, diet, smoking, alcohol intake, diet, calcium intake);
- Clinical features (age and years of menopause, medical history, history of osteoporosis and parental osteoporosis, any prior fractures, prior and concomitant medication, antiresorptive treatment, glucocorticoid treatment, other treatment reducing bone mass);
- FRAX score (as determined by self-reported fracture and radiology evidence and calculated based on the information from questionnaire with/without BMD).

BMD Measurement

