8.3 Sample Size and Power Calculations

The sample size of the study was calculated based on prevalence data per age group several large epidemiological studies [29-32, 36]. As the prevalence of vertebral fractures increases with age, the sample size will be determined as per age group by setting a lower limit for each assumed age-based prevalence rate (Table 8.3.1), using Clopper-Pearson exact method [52] to compute the lower bound of the corresponding 95% CI at a 5% precision. A sample size of 545 at each geographic region will be statistically sufficient to cover all age groups in detecting the prevalence of vertebral fractures, assuming a 5% withdrawal rate for the spinal radiographs in the study. Considering geographic distribution (5 regions), a total sample size of approximately 2700 postmenopausal women aged 50 or above will be enrolled for the study. In addition, this sample size will yield a generally over 90% power at a 0.05 significance level to detect a geographic impact for the fracture prevalence by an odd ratio at 1.40 or 1.50, by using a univariate logistic model in estimating the change in probability.

Assuming a 40% nonresponse rate in population-based studies [56] and 5% ineligibility rate [32], invitation letters will be posted to approximately 4750 women in all regions.

Table 8.3.1 Sample Size Calculation by Age Group based Prevalence

Age group	Sample size	Assumed Prevalence	95% CI Lower Limit
50 - 54	44	5.0%	1.0%
55 - 59	81	7.0%	3.0%
60 - 64	100	12.0%	6.0%
65 - 69	90	16.0%	10.0%
70 - 74	80	20.0%	12.0%
75 - 79	70	23.0%	15.0%
>80	53	37.0%	26.0%

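### The overall prevalence is standardised for age but not for region, so five about equally sized regional samples count by sample share and not by population share

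*Combined protocol and SAP*

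**What the plan says.** The primary objective (Sections 2.1 and 8.1.1) is prevalence in China, and Section 3.1 says the sampling is meant "to represent a geographically generalized Chinese population". Section 3.5 stratifies by seven age groups and by region: "Five (5) regions in China: North, South, Southeast, Southwest, and Central".

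Section 8.3 sets the regional sample from a single age table (Table 8.3.1): "A sample size of 545 at each geographic region will be statistically sufficient to cover all age groups". The total follows: "Considering geographic distribution (5 regions), a total sample size of approximately 2700 postmenopausal women aged 50 or above will be enrolled".

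For the analysis, Section 8.1.1 states: "Point estimates of prevalence rates by overall and geographic region will be adjusted by a nationwide age distribution". The method is direct standardisation to the 2010 census. For the overall rate, Table 8.1.1.1 lists a crude and an age-standardised version and nothing else. Section 8.1.2.1 adjusts osteoporosis prevalence by age in the same way. Section 8.1.1 leaves open standardising to a regional age distribution. No section gives a regional population size, a sampling weight or a region weight.

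**The concern.** Age and region are both stratifiers, and both allocations were chosen for precision and not in proportion to population. The plan undoes the age allocation by standardising to the census. It does not undo the region allocation.

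The headline figure is meant to describe a population in which the five regions need not be equal in size. A region with few older women would then count as much as one with many. Enrolling more women in the same proportions would narrow the interval without removing the error. The optional regional age distribution does not help, because it changes the age mix used within a region and not the region's share of the overall rate.

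**Working it through.** **Inputs from the documents.** Table 8.3.1 sample sizes 44, 81, 100, 90, 80, 70, 53; assumed prevalences 5, 7, 12, 16, 20, 23, 37%; 5% loss of spinal radiographs; five regions; detectable odds ratios of 1.40 or 1.50 (all Section 8.3); 8 to 10 sites (Section 3.2).

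**Reproducing the plan's sample size.** The table sums to 518. 518 / 0.95 = 545.3, which matches 545. 5 × 545 = 2725, which matches approximately 2700. As planned, each region is 545 / 2725 = 20% of the sample and, because one age table serves all regions, 20% of every age group.

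**Weight implied for each region.** Let w_a be the census age weight, and n_ra and p_ra the number and prevalence in region r and age group a. The planned overall rate is

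Σ_a w_a × (Σ_r n_ra p_ra / Σ_r n_ra).

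With n_ra equal across regions, the bracket is the plain mean of five regional rates. The overall rate is then the plain mean of the five age-standardised regional rates, whatever the w_a are. If enrolment is uneven, the weights follow enrolment, which is still not population.

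**Size of the shift.** If the regions share one age structure, the population-weighted rate minus the planned rate is Σ_r (s_r − 0.20) × R_r, where s_r is the population share and R_r the regional rate. The shares are not in the documents, so they are assumed. The 12.5% baseline is also an assumption.

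Odds at 12.5% are 0.1429; × 1.5 = 0.2143; prevalence 17.65%; difference 5.15 points.

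| Regions at OR 1.5 | Planned overall rate | Assumed share | Population-weighted rate | Shift (points) |
|---|---|---|---|---|
| one | 12.5 + 0.20 × 5.15 = 13.53% | 10% | 13.01% | −0.5 |
| one | 13.53% | 15% or 25% | 13.27% or 13.79% | −/+0.26 |
| one | 13.53% | 35% | 14.30% | +0.8 |
| two | 12.5 + 0.40 × 5.15 = 14.56% | 20% jointly | 13.53% | −1.0 |
| two | 14.56% | 60% jointly | 15.59% | +1.0 |
| none | 12.5% | any | 12.5% | 0 |

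**Sensitivity to the baseline.** Section 1.1 cites 15% for women aged 50 or over, and Table 8.3.1 at its own age mix gives 85.98 / 518 = 16.6%. Applying the odds ratio within each age group of Table 8.3.1, with the sample age mix as age weights (an assumption, since the census weights are not given), one divergent region with a share of 10%, 30% or 40% gives shifts of −0.5, +0.5 and +1.0 points at OR 1.40, and −0.6, +0.6 and +1.2 points at OR 1.50.

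**Scale.** With 2700 × 0.95 = 2565 readable radiographs, the simple binomial half-width at 13% is 1.96 × √(0.13 × 0.87 / 2565) = 1.3 points. This ignores clustering in sites. For illustration, assume 9 equal sites (285 women each) and an intraclass correlation of 0.005 to 0.01, neither of which is in the documents. The design effect 1 + 284 × ICC is then 2.4 to 3.8, and the half-width 2.0 to 2.6 points.

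**Cost of weighting.** The Kish factor is 5 × Σ s_r². It is 1.06 with one region at 10% or 30% and the rest equal, and 1.25 with one at 40%. The interval widens by √1.06 to √1.25, or 3% to 12%.

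**The case against.** The strongest reply is that the bias exists only if regions differ, and the documents do not say that they do. The odds ratios of 1.40 and 1.50 in Section 8.3 are effects the sample is said to be able to detect. A reader might take them as what the plan expects, and the text does not support that. Section 1.2 describes vertebral deformity as fairly homogeneous across world regions. That compares continents and countries, so it does not exclude differences within China, but it leaves the condition open. This part of the reply stands.

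Three further points also stand in part.

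- A reader might infer that every region will carry exactly 20% of the result. Section 8.3 calls 545 sufficient and the total approximate, so 20% is the planned share only.
- The larger shifts need shares well away from 20%, and setting them against 1.3 points flatters their importance, because that half-width ignores clustering in sites.
- Equal allocation is a sound choice for the regional rows. Those rows and the age-by-region rates will be reported, so a reader could reweight them.

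None of this supplies a region weight. Visible regional rows do not correct the headline rate. Section 8.1 foresees a separate SAP, which could add the weight, but the present text commits only to age.

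**Conclusion.** The gap is real and should be closed. As written, the overall fracture and osteoporosis rates weight regions by sample share, about 20% each as planned, and are biased for the combined population of the five regions if regional prevalences differ.

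The amount is conditional. It is zero without regional differences and about 0.3 points if one region at OR 1.5 holds 15% or 25%. It is about 0.5 to 1.0 points with one or two such regions and shares well away from 20% per region, on an assumed 12.5% baseline. Using the Table 8.3.1 rates and a 40% share, it reaches 1.2 points.

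Two stronger readings should be resisted. The documents do not show that the reported rate will in fact be wrong by a known amount, since neither the regional shares nor the regional differences are given. Nor would region weighting yield the correct figure for China: Section 3.3 admits only women living in urban communities, and the documents do not say that the five regions cover every province or that sites are drawn at random within a region. Weighting removes one source of bias and leaves those limits in place.

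**What to change.** In Sections 8.1.1 and 8.1.2.1, and in the SAP:

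- Standardise the overall rates to the joint age-by-region census distribution: Σ_r Σ_a W_ra × p_ra, where W_ra is the share of urban women aged 50 or over in age group a in the areas assigned to region r. Whole provincial populations would not match the urban inclusion criterion in Section 3.3.
- Fix before database lock a threshold below which adjacent age groups are merged. The youngest cell has 44 women per region at 5%, or 2.2 expected cases.
- Compute the 95% interval for this weighted estimate. A binomial interval for the pooled count does not describe it.
- Keep age-only standardisation for the region rows, and label the equal-weight pooled rate as a sample summary.
- State that inference is to urban women in the five sampled regions.

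The cost is a province-to-region map, a check that the census source cited in Section 8.1.1 has the urban tables needed, and an overall interval about 3% to 12% wider under the shares assumed above. No new data are collected from participants and the regional allocation is unchanged.
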